Primary outcomes	
Primary outcomes assessed at T2 (change from baseline):
 
(i) Exercise mindset using the Mindset about the Process of Health – Exercise scale. This one-factor scale was developed and validated¹ to assess mindset about the process of engaging in physical activity (e.g., physical activity is difficult/easy, unpleasant/pleasurable, boring/fun). The scale consists of 7 items and is measured on a 4-point scale and scored from 1 to 4, with a higher score reflecting a more appeal-focused mindset about exercise
 
(ii) Osteoarthritis mindsets using the Illness Mindset Inventory. The Illness Mindset Inventory measures three mindsets about the nature and meaning of illness: that it is a catastrophe, manageable, or an opportunity. The scale consists of 20 items measured on a 6-point scale and scored from 1 to 6, with 10 of those questions capturing mindsets about chronic illness. The extent to which a participant endorsed each mindset was obtained by calculating the respective mean scores. A higher score indicates greater agreement with the mindset. This Illness Mindset Inventory is valid and reliable in individuals with knee osteoarthritis². We adapted the scale to focus on mindsets about "knee osteoarthritis" as opposed to "chronic disease."
 
Primary outcomes assessed at T3 (change from baseline):
 
(i) Knee pain using the question, "What was your average osteoarthritis-related pain over the past week?" and measured on an 11-point Numeric Rating Scale (NRS) from 0 (no pain at all) to 10 (the worst pain imaginable)
 
(ii) Physical activity using the Physical Activity Scale for the Elderly (PASE). The PASE asks respondents about the frequency of light, moderate, and strenuous work and leisure activities and is a validated measure of self-reported physical activity for individuals with osteoarthritis³. The scale is scored from 0 to 793 with higher scores indicating higher levels of physical activity.

Secondary Objectives	
Key secondary	Secondary outcomes assessed at T2 (change from baseline):

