
outcomes
	
(i) Knee osteoarthritis knowledge by the Knee Osteoarthritis Knowledge Scale⁴. The Knee Osteoarthritis Knowledge Scale is scored from 11-55 and measures knowledge about osteoarthritis in individuals with knee or hip osteoarthritis
 
(ii) Body mindsets using the Illness Mindset Inventory. In addition to mindsets about chronic illness, the Illness Mindset Inventory measures three mindsets about the nature of the body in the context of a chronic illness: that it is adversarial, responsive, or resilient
 
(iii) Activity adequacy mindsets using the Adequacy of Activity Mindset Measure⁵. This scale was developed to assess mindsets about the adequacy and benefits of one's physical activity as it relates to health. The scale consists of 5 items measured on a 7-point scale and scored from 1 to 7, with a higher score reflecting a more adaptive mindset about the benefits and risks associated with current levels of physical activity.
 
Secondary outcomes assessed at T3 (change from baseline):
 
(i) Knee pain and functioning using the Short version of the Western Ontario and McMaster Universities Arthritis Index (shortMAC). The shortMAC is a disease-specific 12-item measure of knee symptoms and has shown to be valid and reliable in patients with knee osteoarthritis⁶. We evaluated the measure divided into two subscales: pain and function
 
(ii) Perceived need for surgery using the single question, "How likely do you think you are of needing knee replacement surgery in the future?" It was answered on the Likert scale from 1 (very unlikely) to 5 (very likely)
 
(iii) Chosen symptom management strategies using the single question, "Which of the following are ways in which you manage and/or improve your osteoarthritis symptoms? Please select all that apply." It was answered via multiple choice with a multiple-selection option. The options available were the most commonly identified responses as determined by a previous study⁷
 
(iv) Fear of movement using the Brief Fear of Movement Scale for Osteoarthritis⁸. The Brief Fear of Movement Scale for Osteoarthritis is a 6-item scale validated to assess fear of movement in individuals with osteoarthritis
 
(v) Arthritis self-efficacy using the Arthritis-Self Efficacy Scale. This scale is scored from 1 to 10, with higher scores indicating greater self-efficacy, and was divided into the "pain" and "other symptoms" subscales
 
(vi) Physical and Mental Health using the PROMIS v.1.1 Global Health Short Form⁹. This scale is a 10-item survey that measures overall physical function, fatigue, pain, emotional distress, and

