	
Osteoarthritis is a 6-item scale validated to assess fear of movement in individuals with osteoarthritis
 
(v) Arthritis self-efficacy using the Arthritis-Self Efficacy Scale. This scale is scored from 1 to 10, with higher scores indicating greater self-efficacy, and was divided into the "pain" and "other symptoms" subscales
 
(vi) Physical and Mental Health using the PROMIS v.1.1 Global Health Short Form⁹. This scale is a 10-item survey that measures overall physical function, fatigue, pain, emotional distress, and social health in healthy and clinical adult populations¹⁰. We evaluated the measure divided into its two subscales: physical health and mental health¹¹.

--	--

Research Hypotheses

Hypothesis 1. A digital education and mindset intervention will significantly improve mindsets about the process of exercising and osteoarthritis among adults aged ≥ 45 years with knee osteoarthritis compared to an active comparison education intervention and no-intervention immediately post-intervention.

Hypothesis 2. A digital education and mindset intervention will significantly reduce knee pain and increase physical activity levels among adults aged ≥ 45 years with knee osteoarthritis compared to an active comparison education intervention and a no-intervention control group one-month post-intervention.

Hypothesis 3. A digital education and mindset intervention will significantly improve knee osteoarthritis knowledge and mindsets about activity adequacy and the body among adults aged ≥ 45 years with knee osteoarthritis compared to an active comparison education intervention and a no intervention control group immediately post-intervention.

Hypothesis 4. A digital education and mindset intervention will significantly improve knee pain and function, perceived need for surgery, symptom management, arthritis self-efficacy, fear of movement, physical health, mental health, among adults aged ≥ 45 years with knee osteoarthritis compared to an active-comparator education group and a no-intervention control group one-month post-intervention.

Key Personnel

Trial Coordinator

[name], [contact]
 Department of Bioengineering
 Stanford University, Stanford, California, USA

Statisticians

[name]
Department of Statistics
Stanford University, Stanford, California, USA

[name]
Department of Statistics
Stanford University, Stanford, California, USA

Trial Design

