We will randomize 505 individuals aged ≥ 45 years with knee osteoarthritis into one of three groups with 1:1:1 group allocation: the Mindset Group (participants receive a digital mindset intervention to improve mindsets about osteoarthritis and exercise), the Education Group (Participants receive a series of osteoarthritis education videos and reflective questions that matches the digital mindset intervention in duration and attention), or the No-Intervention Group (participants take the same surveys as the other groups at the same time points, but do not receive any additional content). Participants will complete an initial baseline survey and be randomized one week later. Those randomized to the Mindset and Education Groups will have one week to complete the self-paced online programs. All groups complete osteoarthritis knowledge and mindset surveys at this timepoint. One-month later, participants will receive a follow-up questionnaire.

Study Setting

The study will be conducted entirely online.

Eligibility Criteria

Inclusion Criteria:

- Over 45 years of age
- Self-reported doctor's diagnosis of knee osteoarthritis OR meets the National Institute for Health and Care Excellence osteoarthritis clinical criteria (activity-related knee pain and no knee morning stiffness lasting ≥ 30 minutes)
- Knee pain for at least 3 months
- Ability to walk unaided
- Can read and write in English
- Consistent internet access
- Willingness and ability to comply with the study requirements

Exclusion criteria:

- Past total knee arthroplasty or scheduled surgical procedure on any back or

- lower limb with osteoarthritis within the next 12 months
- Recent serious injury (within the past 2 months) on the knee(s) with osteoarthritis
- Any condition making it unsafe to participate in physical activity
- Intra-articular therapy within the past 6 months (e.g. injections such as corticosteroids and hyaluronic acid)
- Participates in physical exercise for 30 minutes or more 5 days per week

Interventions

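### The primary knee-pain item does not name the knee, so osteoarthritis pain from other joints can enter the score and could weaken or blur a knee-pain conclusion

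*Combined protocol and SAP*

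**What the plan says.** Supplement 1 Table 2 lists knee pain as the first primary outcome at T3, scored 0 to 10 and analysed as change from baseline. The item reads "What was your average osteoarthritis-related pain over the past week". Hypothesis 2, under Research Hypotheses, states that the intervention "will significantly reduce knee pain and increase physical activity levels".

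Other instruments in the same table do name the site. For the Illness Mindset Inventory the investigators write "We adapted the scale to focus on mindsets about" and then specify knee osteoarthritis. The perceived-need-for-surgery question asks about knee replacement. Of the secondary T3 measure the table says "The shortMAC is a disease-specific 12-item measure of knee symptoms", and its pain and function subscales are evaluated separately.

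The Eligibility Criteria require knee osteoarthritis (a self-reported diagnosis or clinical criteria) and at least 3 months of knee pain. Osteoarthritis at another joint is not an exclusion. The surgery exclusion covers scheduled procedures on any back or "lower limb with osteoarthritis within the next 12 months", so it allows for disease at more than one site.

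The Sample Size section counts the intervention a success if NRS pain, PASE or both improve.

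**The concern.** The label and the hypothesis are about the knee, but the question is about osteoarthritis pain wherever it occurs. A participant who also has hip, hand or back osteoarthritis can answer accurately about those joints. Someone who enters on the clinical knee criteria, with a doctor's diagnosis only for another joint, might take the question to mean that other joint.

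Two things are at stake. If pain elsewhere does not respond to the programme, it adds an unresponsive part to the score and a knee effect looks smaller than it is. If pain elsewhere does respond, a positive result is real but cannot be reported as a knee-pain effect. In both cases one of the two outcomes that decide success may not measure what Hypothesis 2 states. Pain supplies two of the four Bonferroni comparisons in Statistical Methods.

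**Working it through.** **Inputs from the documents.** Sample Size: 139 per group; SD 70.28 for PASE and 1.67 for pain; PASE target 26 points; pain target 2 points; presumed effect 0.3 SD; 80% power. Statistical Methods: threshold 0.0125 for each of four comparisons. The a priori power analysis rejects in one direction only.

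**The plan's own figure.** n = 2·SD²·(z_α + z_power)² / Δ². With one-sided 0.0125 (z = 2.241) and 80% power (z = 0.842): 2 × 70.28² × (3.083)² / 26² = 138.9, so 139 per group. The stated size reproduces. It was set by PASE.

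**Standard error for pain.** 1.67 × √(2/139) = 0.2003 points. With a two-sided 0.0125 test (z = 2.498), the smallest difference detectable with 80% power is 0.2003 × (2.498 + 0.842) = 0.67 points.

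**Dilution model (assumed).** A fraction q of the rated change comes from joints with no treatment effect, and the SD stays at 1.67. A knee effect D then appears in the score as (1 − q)·D, and

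power = Φ[(1 − q)·D / 0.2003 − 2.498].

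The documents give no value for q; 0, 20% and 40% are illustrations.

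For D = 0.3 × 1.67 = 0.501 points:
- q = 0: Φ(2.501 − 2.498) = 0.50
- q = 20%: Φ(2.001 − 2.498) = 0.31
- q = 40%: Φ(1.501 − 2.498) = 0.16

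For D = 2 points:
- q = 40%: Φ(5.990 − 2.498) = Φ(3.49), above 0.999
- q = 60%: Φ(3.994 − 2.498) = 0.93

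| True knee effect (points) | q = 0 | q = 20% | q = 40% |
|---|---|---|---|
| 0.50 (0.3 SD) | 0.50 | 0.31 | 0.16 |
| 0.67 (80% power undiluted) | 0.80 | 0.57 | 0.31 |
| 1.0 | 0.99 | 0.93 | 0.69 |
| 2.0 (plan's pain target) | >0.999 | >0.999 | >0.999 |

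**Sidedness.** With the one-sided 0.0125 test that reproduces 139, z is 2.241. The 0.50-point row becomes Φ(0.260) = 0.60, Φ(−0.240) = 0.40 and Φ(−0.741) = 0.23. The level rises but the pattern is the same.

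**Reading the table.** Dilution would matter for an effect near the presumed 0.3 SD and would not matter at 2 points. The 50% power at 0.3 SD with no dilution is a separate sample-size matter, not a result of the item's wording.

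**The case against.** The strongest reply is that nothing shows participants will rate other joints. Everyone enrolled has had knee pain for at least 3 months and meets knee-based criteria, and the study is about knee osteoarthritis. The full survey text is not in the documents and could direct the answer to the knee. The surgery exclusion shows that disease elsewhere was thought of, not that it is common in the sample. This stands: entry of other-joint pain is possible, not demonstrated.

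A reader might go further and infer that the effect is diluted and the pain comparison underpowered because of the wording. The documents do not support that. Both q and the absence of any effect on other joints are assumptions. The programme targets mindsets about osteoarthritis and exercise, so pain elsewhere may move in the same direction and dilution could be small or absent. If the SD of 1.67 came from this same item, which is not stated, any extra variability is already in it. It would also be wrong to apply an effect of 0.37 SD to pain: that is the PASE figure, 26/70.28.

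Two further points limit the harm. Randomisation should balance other-joint disease across arms, so the issue is what the score measures and how sensitive it is, not imbalance between arms. And the shortMAC pain subscale gives a knee-specific result at T3. But it is secondary and does not define success, so it does not remove the mismatch in the primary outcome.

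**Conclusion.** The mismatch is established from the text: a primary outcome labelled knee pain, a hypothesis about knee pain, an item that names no joint, and eligibility that admits osteoarthritis elsewhere. The supportable conclusion is that other-joint pain can enter the score and could weaken a knee-pain finding or make it non-specific.

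The size is unknown. Under the assumed model the loss of power is large at 0.3 SD and negligible at the plan's 2-point target. Those figures rest on an assumed q, no effect on other joints, a fixed SD of 1.67, 139 completers per group and a two-sided 0.0125 test. This is a construct-validity gap in an outcome that helps decide the trial. It is not a numerical error, and the sample-size arithmetic is unaffected. It is worth correcting because the correction is nearly free.

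**What to change.** Before enrolment opens (April 2023 in Supplement 1 Table 1), insert the word *knee* directly before *osteoarthritis-related* in the item, identically at baseline and T3 in all three arms. If the survey already carries a knee-only instruction ahead of the item, print that instruction in the protocol.

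If the item must stay as it is, relabel the outcome and reword Hypothesis 2 as osteoarthritis-related pain, and base any knee-specific pain conclusion on the shortMAC pain subscale.

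The cost is one word in an online survey and a minor ethics amendment, with no added participants or burden. The downside is that the SD of 1.67 may not carry over exactly if it came from the unmodified item. The one-word change also leaves open which knee is rated when both are affected, and the protocol should say so either way.

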The efficacy of the mindset intervention will be deemed successful if enhancements in either or both key outcomes, namely pain intensity (NRS) or physical activity levels (PASE), are observed. Anticipating modest effect sizes between the mindset and educational cohorts, we conducted a preliminary power analysis, similar to prior online education studies for knee osteoarthritis^{12,13}, using G*Power 3.1 with a presumed effect size of 0.3 (see below). This analysis involved comparing the mindset group against both the education and no-intervention groups, leading to four distinct comparisons. These assessments are planned to be executed at a 5% significance level, aiming for an 80% probability of discerning a noticeable improvement in delta. Based on Boswell et al.⁷, we estimated the standard deviations for PASE and pain at 70.28 and 1.67, respectively. A 26-point difference in PASE was selected as the target delta. While no clinically significant benchmarks for PASE has been established, the intervention's focus on promoting walking and moderate exercise led us to define this delta as the equivalent shift in walking and light exercise frequency from “seldom” (<1 hour per day) to “sometimes” (1-2 hours per day), as per the PASE scale, giving a goal of 26 points. This determination necessitates a sample size of 139 participants per group, totaling 417. To compensate for an anticipated 20% dropout rate, we plan to enroll 501 participants. This sample size is adequately powered to detect a clinically relevant difference of 2 points in NRS pain¹⁴.

A priori power analysis

[name]

11/29/2022

Let, y_i^b represents outcome at baseline and y_i^f represents outcome at follow-up for i^{th} person in treatment group, and \bar{y}^b and \bar{y}^f represents respective means. Similarly, x_i^b represents outcome at baseline and x_i^f represents outcome at follow-up for i^{th} person in control group, and \bar{x}^b and \bar{x}^f represents respective means.

Assumption: Let $x_i^f - x_i^b \sim \mathcal{N}(\Delta_1, \sigma^2)$ and $y_i^f - y_i^b \sim \mathcal{N}(\Delta_2, \sigma^2)$.

Let's say $\Delta = \Delta_2 - \Delta_1$, we want to test the hypothesis

$$H_0 : \Delta = 0$$

$$\text{v/s } H_1 : \Delta > 0$$

Under H_0 , $T = (\bar{y}^f - \bar{y}^b) - (\bar{x}^f - \bar{x}^b) \sim \mathcal{N}(0, 2\sigma^2/n)$. We reject H_0 if $\frac{T}{\sqrt{2\sigma^2/n}} > z_{1-\alpha}$. We want n so that power at Δ is $1 - \beta$, i.e.,

[figure not shown]

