$$P_{\Delta} \left(\frac{T}{\sqrt{2\sigma^2/n}} > z_{1-\alpha} \right) \geq 1 - \beta$$

which is equivalent to

$$n \geq \frac{2\sigma^2(z_{1-\alpha} + z_{1-\beta})^2}{\Delta^2}$$

[figure not shown]
For our analysis, we choose $\alpha = 0.05$, and try four different values of β , 0.05, 0.10, 0.15, and 0.20. We estimate σ from pilot data.

Outcome variable, PASE

[figure not shown]
[figure not shown]

sigma = 70.27939

A priori sample size analysis for outcome variable, PASE

[figure not shown]

Pain Scores

sigma = 1.670426

A priori sample size analysis for outcome variable, pain

Recruitment

Participants will be recruited through paid online and social media advertising and local flyer postings.

Allocation

We will use the randomizer function in Qualtrics to randomize participants into one of three groups (1:1:1): the Mindset Group, the Education Group (active comparison), or the No-Intervention Group (control).

Blinding (Masking)

During the informed consent process, participants will be informed that the purpose of the study is to understand the effect of a new online osteoarthritis program and that they will be randomized to either a no-intervention group or one of two different sets of videos and reflective questions. Participants will be aware of whether they are randomized to an online program; however, the differences in content between the two programs and the hypotheses of the study will not be revealed. The biostatistician performing the data analysis will be blinded to the group labels.

Data Collection, Management, and Access

All data will be collected through the Qualtrics online survey software. Qualtrics encrypts all transmitted data using Transport Layer Security and hosts data on data centers that are independently audited using the industry standard SSAE-18 method. Stanford University has a Qualtrics license for research use, and data obtained from the Qualtrics platform can only be accessed through a secure login. Data will be exported to Microsoft Excel and securely stored for use by the research team. Only after de-identification may the data be shared outside of the research team.

Missing Data

Participants who did not complete a survey entirely were removed from the study and not sent the follow-up survey. Each question of each survey was “force response,” meaning that if a participant completed the survey, no answers would be missing from the response. Thus, no methods for missing data were implemented.

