where \bar{X} is the mean of changes in the first group and \bar{Y} is the mean of the changes in the second group, s_{pooled} is the pooled standard deviation from the two groups. We assume that there were m people in the first group and n people in the second group. After calculating the t-statistics, the p-values will be computed to estimate the statistical significance of differences in changes between groups. We will perform Bonferonni correction for the four comparisons (e.g., the mindset group vs. the education group and the mindset group vs. the no-intervention group for pain and physical activity at one-month follow-up), which adjusts the significance threshold to $P = 0.0125$. The comparison of the education group to the no-intervention group will not be a primary comparison.

Data Monitoring

The trial coordinator will provide ongoing project oversight and will meet regularly with the senior investigators throughout the project period to provide study feedback including recruitment, retention, and adverse events. During the study, participants have access to email the study coordinator at any time to report adverse events.

Harms

The potential harms associated with this study include psychological complications resulting from the assessments or mindset and education programs or medical risks due to increasing physical activity levels. There is a small risk that individuals completing psychological questionnaires may become distressed, but there is no evidence of resulting psychological dysfunction. We performed pilot testing of the program and questionnaires in which there was no evidence of psychological complications or the risk of such complications. Further, while the program presents the benefits of physical activity, no specific programs are requested for participation and participants are encouraged to go slow and listen to their bodies.

Therefore, no harm or adverse events are foreseen in this study. However, if a complaint or adverse event arises, the research team will discuss and take appropriate action to manage the issue. Any serious adverse event or harm reported by participants will be recorded and reported.

Research Ethics Approval

The study protocol, consent form, and recruitment material will be approved by the Stanford University Research Compliance Office Institutional Review Board.

Protocol Amendments

Protocol amendments will be documented and reported.

Consent Or Assent

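### The success rule names no comparator, so a win over No-Intervention alone meets it, while Hypothesis 2 claims benefit over both Education and No-Intervention

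*Combined protocol and SAP*

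**What the plan says.** - **Success rule (Sample Size).** "The efficacy of the mindset intervention will be deemed successful if enhancements in either or both key outcomes", pain NRS or PASE, are observed. The sentence does not say against which group.
- **Tests (Sample Size).** The power analysis is described as "comparing the mindset group against both the education and no-intervention groups, leading to four distinct comparisons", and adds: "These assessments are planned to be executed at a 5% significance level".
- **Multiplicity (Statistical Methods).** "We will perform Bonferonni correction for the four comparisons", giving a threshold of 0.0125 for each. Education versus No-Intervention is not a primary comparison. The sidedness of the t-tests is not stated.
- **Hypothesis 2 (Research Hypotheses).** The intervention "will significantly reduce knee pain and increase physical activity levels" "compared to an active comparison education intervention and a no-intervention control group one-month post-intervention". Both the outcomes and the comparators are joined by 'and'.
- **Role of the arms (Trial Design; Blinding).** The Education content "matches the digital mindset intervention in duration and attention". No-Intervention participants complete surveys only. "Participants will be aware of whether they are randomized to an online program".

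**The concern.** The rule and the hypothesis are different claims. Four stand-alone tests with a four-way Bonferroni split are what one would write if any single win were enough. Hypothesis 2 needs Mindset to beat both controls.

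The difference matters because of what each control can show. Pain and PASE are self-reported, and participants know whether they were given a program. A win over No-Intervention alone could come from attention, expectancy or generic osteoarthritis education. Only the Education contrast separates the mindset content from these. Followed as written, the rule lets the trial announce that the mindset intervention works in a case where it is no better than the education videos.

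The same mismatch affects alpha. If both controls must be beaten, the two tests on one outcome form an intersection-union test, and no split over comparators is needed.

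**Working it through.** **Inputs from the plan (Sample Size).** PASE SD of change 70.28; target difference 26; 139 per group; power 80%; alpha 0.05 over four comparisons; one-sided alternative in the power derivation. Standardised difference: d = 26/70.28 = 0.370.

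**Assumptions not in the plan.** Correlation between the two outcomes of 0 to 0.5, and equal true effects against both controls in the power scenarios. The shared Mindset arm with 1:1:1 allocation gives a correlation of 0.5 between the two comparisons on one outcome.

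**1. Reproduce 139.** The plan's formula is n = 2σ²(z₁₋α + z₁₋β)²/Δ². With one-sided alpha 0.05/4 = 0.0125:

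n = 2 × 70.28² × (2.241 + 0.842)²/26² = 138.9, so 139.

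The critical value 2.241 is also that of a two-sided 0.025 test. A two-sided 0.0125 test has critical value 2.498 and would need 163.

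**2. The rule when Mindset equals Education.** The standardised difference from No-Intervention on PASE is λ = d√(n/2) = 0.370 × √69.5 = 3.084. At two-sided 0.0125, power for that one test is Φ(3.084 − 2.498) = 72.1%. Simulation of all four tests (400,000 trials, 139 per group) gives the chance that at least one favours Mindset:

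| Mindset = Education, both better than No-Intervention | Any of four significant |
|---|---|
| PASE only, d = 0.37 | about 72% |
| Both outcomes, d = 0.37, outcome correlation 0 / 0.3 / 0.5 | 92% / 89% / 86% |
| Both outcomes, d = 0.30, outcome correlation 0 / 0.3 / 0.5 | 75% / 70% / 67% |

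A win over Education occurs in only about 1.2% of these trials. If 0.0125 is one-sided, the PASE test against No-Intervention alone succeeds in Φ(3.084 − 2.241) = 80.0%.

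**3. Error if both controls must be beaten.** In the same scenarios, the chance of beating both controls on at least one outcome, each test at two-sided 0.025, is 2.3-2.5%. It stays there when the effect against No-Intervention is made very large (d = 5). Splitting alpha over the two outcomes is therefore enough.

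**4. Power for the claim in Hypothesis 2, PASE, 139 per group.** True difference of 26 points against both controls; the probability of beating both is bivariate normal with correlation 0.5.

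| Per-test level | One comparison | Both comparators | n per group for 80% against both |
|---|---|---|---|
| Two-sided 0.0125 | 72.1% | 58.3% | 197 |
| Two-sided 0.025 (= one-sided 0.0125) | 80.0% | 68.8% | 170 |
| Two-sided 0.05 (= one-sided 0.025) | 87.0% | 78.6% | 144 |

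At d = 0.30 the middle column of joint power reads 33.5%, 44.2% and 56.4%. For a 2-point pain difference (2/1.67 = 1.20 SD), power is about 100% at every level, so any loss falls on PASE or on smaller pain effects.

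**5. Cost of the stricter rule.** If Mindset beats both controls by d = 0.37 on both outcomes (correlation 0.3, two-sided tests), any-of-four at 0.0125 succeeds in 96.4% of trials. Both comparators at 0.025 on at least one outcome succeeds in 86.7%.

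**The case against.** **No sentence says a lone win over No-Intervention is enough.** This is correct. The surrounding text anticipates an effect between Mindset and Education, and each comparison is listed separately, so a null result against Education would be visible to readers. What remains is that the rule still permits the claim by silence, and nothing in the plan blocks it.

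**Error is controlled.** Also correct. A reader might infer that 72% or 86-92% is a false-positive rate. It is not: it is the power to detect a real benefit over No-Intervention, and the four-way Bonferroni controls family-wise error for an any-of-four claim. The scenario also departs from Choice of comparator, where the education content is expected to have no effect. It is a stress test of the conclusion, not a forecast.

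**The threshold of 0.0125 may waste nothing.** A reader might infer that 0.0125 is simply too strict and that 0.025 restores the planned 80%. The documents do not support this without a statement of sidedness. The only alternative written out is one-sided, and at one-sided 0.0125 the plan already has 80% per comparison and 68.8% against both. The four-way split also buys something: a claim against Education that does not depend on the No-Intervention result.

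**Hypothesis 2 joins the outcomes with 'and' too.** Read strictly, it needs all four wins and no alpha split. It could also be read as a scientific expectation covering separate comparisons, rather than a decision rule. Either way, the plan has to say which wins support which claim.

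**Conclusion.** The concern holds as a mismatch between the success rule and Hypothesis 2. As written, the trial could declare the mindset intervention efficacious on a win over No-Intervention alone. That would happen in about 72% of trials if Mindset and Education share a 26-point PASE benefit and pain is unaffected, and in 86-92% if pain shifts by the same standardised amount. These figures assume two-sided tests at 0.0125, 139 per group and, where both outcomes shift, an outcome correlation of 0.5 to 0.

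The power consequence is conditional. If both comparators are required and tests are two-sided, moving from 0.0125 to 0.025 raises joint power on PASE from 58% to 69%. If 0.0125 is one-sided, the critical value already equals two-sided 0.025, and a gain (69% to 79%) comes only from moving to one-sided 0.025. In neither case does 139 per group give 80% power against both controls at an alpha split over two outcomes and an overall two-sided 0.05, which would need 170.

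**What to change.** 1. State that efficacy under Hypothesis 2 on an outcome requires significant wins over both Education and No-Intervention on that same outcome.
2. State how a win over No-Intervention alone will be reported: better than no program, not shown better than education.
3. Align the outcome wording. Either Hypothesis 2 allows pain or PASE, or the success rule requires both.
4. State the sidedness of the t-tests and set alpha to match. If either outcome suffices and both comparators are required, an overall two-sided 0.05 gives two-sided 0.025 per outcome, with no further split over comparators. If both outcomes are also required, no split is needed.

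Testing No-Intervention first and Education second within each outcome is one valid way to keep a fallback claim against No-Intervention, but it is optional.

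The change is to wording only and needs no extra participants. The price is a lower chance of declaring overall success, about 96% to 87% under the conditions in step 5 of the working. There would also be no claim of efficacy under Hypothesis 2 on an outcome where either comparison fails.
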